1 PURPOSE

The objective of this prospective, multi-center, two-arm randomized, blinded study is to demonstrate the safety and efficacy of the LUM Imaging System (LUM015 imaging agent in conjunction with the LUM Imaging Device and decision software), in identifying residual cancer in the lumpectomy bed of female breast cancer patients. The size of this study is driven by the necessary number of truth standard positive events; therefore, we propose an event-driven clinical study. Patients will be enrolled until 70 truth standard positive events are reported, up to a maximum of 450 patients.

2 SUMMARY OF ENDPOINTS

2.1 Three co-primary endpoints

- Ratio of patients who have **residual cancer** found in at least one Lumicell-guided shave (also known as therapeutic shave) among all patients. **Residual cancer** is defined as tumor found by pathology in a therapeutic shave after the SOC surgical procedure is completed; that is, tumor that current SOC surgery failed to remove.
- Instrument diagnostic accuracy measured as two separate endpoints of **sensitivity** and **specificity** on a per-tissue basis.

2.2 Secondary endpoints

- a. Proportion of patients with positive margins after standard of care breast-conserving surgery who have a LUM Imaging System signal in the cavity above the threshold as defined by the tumor detection algorithm (i.e., a positive LUM signal).
- b. Proportion of subjects with pathology-positive margins after standard of care breast-conserving surgery for whom additional LUM Imaging System-guided shaves resulted in pathology-negative margins among patients with positive margins. Note: This endpoint also estimates the potential reduction in re-excision surgeries following standard of care breast-conserving surgery that resulted from a positive SOC margin.
- c. Proportion of subjects with pathology-positive margins after standard of care breast-conserving surgery for whom additional LUM Imaging System-guided shaves resulted in pathology-negative margins among all patients.
- d. Ratio of patients with negative margins after the SOC procedure who have residual cancer found in at least one Lumicell-guided (or therapeutic) shave among patients with negative margins.
- e. Ratio of patients with negative margins after the SOC procedure who have residual cancer found in at least one Lumicell-guided (or therapeutic) shave among all patients
- f. Mean and median incremental volume (in cubic centimeters) of tissue removed from therapeutic shaves: For each patient, absolute shave volume will be calculated as length (c) × width (c) × depth (c) for each therapeutic shave with the sum by patient of all therapeutic shaves. Subjects with no therapeutic shaves taken will have a therapeutic shave volume of 0cc.
- g. Mean and median contribution of therapeutic shave volume to total tissue removed.
- h. Comparison of adverse events in subjects that have at least one therapeutic shave versus subjects that have no therapeutic shaves.

- i. Average number of therapeutic shaves taken per subject overall and by type of SOC lumpectomy procedure (i.e., lumpectomy with comprehensive shaves vs. lumpectomy with or without selective shaves).
- j. Percent of device failures that led to failure of using the LUM Imaging System to capture data.
- k. Rate of re-excision procedures as a result of a positive margin status following SOC (control arm) and LUM Imaging procedures (device arm).
- l. Number of re-excisions for each patient
- m. Number of re-excisions recommended
- n. Collect exploratory data on tissue types found in therapeutic shaves.
- o. Collect exploratory data on patient reported outcome measures (PROMs).
- p. Adverse events stratified by severity and relatedness to drug/device.
- q. Serious adverse events stratified by severity and relatedness to drug/device.
- r. Adverse events by preferred term (sorted by descending occurrences for each preferred term).
- s. Summary of adverse events, overall and split by expectedness to drug/device.

3 BACKGROUND

3.1 Study disease

For breast cancer lumpectomies, the presence of residual cancer cells left in the tumor bed after initial resection is inferred by post-operative margin assessment of the resected tissue by a pathologist. For invasive carcinoma and ductal carcinoma in situ (DCIS), a positive margin is defined as having tumor present at the inked side of the outermost surface of the lumpectomy specimen [1, 2]. However, according to the Society of Surgical Oncology (SSO), for negative margins of less than 2mm in patients with DCIS, clinical judgment is recommended to determine the need for a second surgical procedure [2]. Positive lumpectomy margins are the most important risk factor for local recurrence of breast cancer [1-5] and dictate that a second surgical procedure be performed to obtain tumor-free margins. The rates of close or positive margins have been reported between 17 to 59% [6-10]. Among the more than 318,000 women expected to be diagnosed with breast cancer in the US in 2017, approximately 200,000 underwent lumpectomy and approximately a third required additional surgery for positive margins [11]. Thus, a diagnosis of positive margins indicates that additional treatments are needed. This places a heavy burden on patients and adds significant cost to the healthcare system.

3.2 Rationale

Achieving negative margins during tumor excision is critical to assure that all or most of the cancer has been removed from the patient. Current standard of care dictates that tissue removed during surgery is analyzed post-operatively for tumor histology and margin assessment by a pathologist as described above. This procedure is time consuming, often requiring 7-10 days of pathology testing after the operation before margin status is known. In addition, this process is prone to sampling errors, as only a finite number of tissue slices can be examined, meaning that only a small fraction of the lumpectomy margin surface is assessed, < 1% of lumpectomy surface area by some estimates [2]. Thus, a safe method to directly assess the entire tumor bed intraoperatively and identify residual microscopic disease for immediate resection intraoperatively would be highly beneficial for patients.

Lumicell has developed the LUM Imaging System, which consists of a fluorescence-based imaging agent (LUM015), a hand-held, wide-field detector (LUM Imaging Device) that can image the lumpectomy cavity in seconds, and a tumor detection algorithm that highlights regions suspected to contain cancer and displays them on a computer monitor. The LUM Imaging system is intended to be used to scan the lumpectomy cavity walls intraoperatively after the resection of the main lumpectomy specimen.

The purpose of the Lumicell Imaging System is to enable surgeons to achieve negative margins during the initial surgery and eliminate or reduce the need for re-excision surgeries when compared with current standard of care procedures. Lumicell's system images the entire lumpectomy cavity surface in vivo, overcoming tissue handling and sampling limitations of standard pathology analysis of resected tissue. The LUM Imaging System provides real-time feedback to the surgeon about the status of the lumpectomy cavity walls.

The LUM Imaging System has been tested in a two-phase Feasibility Study at the Massachusetts General Hospital. There were 15 patients in Phase A and 45 patients in Phase B in the study. Of the 11 Lumicell imaged subjects for whom a pathology positive margin followed SOC, the LUM Imaging Device detected 9 (82%) of the subjects with residual cancer in the cavity. A multi-site Feasibility Phase C study is being conducted to refine and verify the tumor detection algorithm and to complete hands on training of surgeons and clinical staff.

3.3 Definitions

3.3.1 Definitions of excised tissue

- **Main specimen:** also known as the “lump” or main mass, refers to the primary piece of tissue removed during a lumpectomy. Typically, this is the largest piece of tissue removed and it is intended to contain most of the tumor.
- **Shave types:** pieces of tissue removed from the lumpectomy cavity walls after the main specimen is removed. In this study, we define three different types of shaved cavity margins (SCMs) below.
 - **Selective shaves:** shaved cavity margins removed from a specific location of the lumpectomy cavity wall based on intraoperative analysis of the **intact main specimen** by methods including X-ray imaging, ultrasound imaging, palpation, frozen sections or visual examination. Selective shaves precede all other SCMs described below.
 - **Comprehensive shaves:** shaved cavity margins removed from *all* available surfaces of the lumpectomy cavity walls after resection of the specimen based on the SOC for that surgeon/site
 - **Therapeutic shaves:** shaved cavity margins removed following the guidance of the LUM Imaging System; may also be referred to as Lumicell-guided shaves.

3.3.2 Definition of standard lumpectomy procedure used in this protocol

Breast conserving surgeries may vary between surgeons and institutions. However, most surgical practices perform what is defined in this protocol as a “**standard lumpectomy procedure**”. This procedure consists of the surgeon's best attempt to remove the main specimen with grossly negative margins and may be followed by the removal of **selective shaves** (see definition above). Some institutions have implemented additional margin management techniques such as comprehensive shaves, as defined above, to try to lower the rates of positive margins and re-

LUMICELL CONFIDENTIAL

This document is confidential. Do not disclose or use except as authorized.

excision [12, 13]. **Table 1** outlines the surgical procedure options that will be allowed in this study to support the primary and secondary endpoints.

Table 1: Surgical procedures to be included in the SOC arm of this clinical study.

SOC procedure	Description	Basis for margin assessment
A. Standard lumpectomy procedure: main specimen followed by selective shaves	Most sites in the US practice this procedure. The main specimen is removed and some selective shaves may be removed based on palpation, X-ray imaging, frozen sections or visual inspection of the intact main specimen .	Outermost surface from a given orientation that can come from the main specimen or a selective shave when a shave exists.
B. Standard lumpectomy procedure followed by comprehensive cavity shaves	After the standard lumpectomy procedure, a cavity shave is removed from all the available orientations. A shave from anterior or posterior may not be removed if no breast tissue remains at these surfaces.	Outermost surface from a given orientation that can come from the main specimen or a comprehensive shave when a shave exists.

3.3.3 Definition of endpoints

3.3.3.1 Definition of positive margins

For this protocol, positive margins are defined using the latest consensus from the Society of Surgical Oncology as follows:

- For invasive cancer with or without associated ductal carcinoma in situ (DCIS): cancer cells or DCIS present on ink [1]
- For pure DCIS lesions: DCIS present less than 2 mm from the ink [2]

3.3.3.2 Definition of re-excisions

A re-excision is defined as a surgical procedure performed in the ipsilateral breast following the primary lumpectomy because of positive margins found from the initial lumpectomy procedure. The re-excision procedure can be a separate surgical procedure to excise further breast tissue or a mastectomy.

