15.1 Analysis Populations

- Safety (SAF) Population: the safety population includes all subjects who received study drug (LUM015).
- Modified Intent To Treat (mITT) population: includes the subjects in SAF, but excluding subjects who are not able to be imaged with the LUM Imaging System. The mITT population will be used as the primary analysis population for the three co-primary efficacy endpoints and efficacy analysis of the secondary endpoints.
- Per-Protocol Population: Includes mITT subjects who complete all study evaluations and are without any major protocol deviations that may impact data collection or efficacy analysis. A sensitivity analysis of the primary and secondary efficacy endpoints will be conducted using the per-protocol analysis set.

15.2 Definition of truth standard for diagnostic performance evaluation (sensitivity and specificity)

We propose to use a hierarchical approach to determine the truth standard as therapeutic shaves were taken only when the LUM imaging system signaled positive for potential residual tumor. The highest truth standard is whether pathology finds cancer in a tissue shave removed from the area that was imaged in the cavity. When a shave does not exist, then whether tumor is found in a re-excision surgery is considered as the truth standard. When neither a shave nor a second surgery exists for a given orientation that was imaged, the margin assessment of that orientation is used as truth standard. **Error! Reference source not found.** shows a schematic for determination of the truth standard.

LUMICELL CONFIDENTIAL

This document is confidential. Do not disclose or use except as authorized.

[figure not shown]

Figure 6: Definition of truth standard to evaluate the LUM Imaging System diagnostic performance.

When the therapeutic shave is not available and the follow-up surgery is performed, only the pathology from the first-time re-excision at the tissue/orientation level will be used for hierarchical sensitivity/specificity evaluation.

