3.2.2 Sensitivity and specificity

The instrument diagnostic accuracy is measured by sensitivity and specificity on a per-tissue basis. Because a LUM-guided shave does not exist when a negative LUM image is indicated we propose a hierarchical approach to determine the truth standard as depicted in Figure 2. The highest truth standard is whether pathology finds cancer in a tissue shave removed from the area that was imaged in the cavity. When a shave does not exist, then whether tumor is found in a re-excision surgery is considered as the truth standard. When neither a shave nor a second surgery exists for a given orientation that was imaged, the margin assessment of that orientation is used as truth standard. We believe that the hierarchical approach outlined to determine the truth standard is the most meaningful and practical assessment of device accuracy to predict the presence of cancer in the cavity.

LUMICELL CONFIDENTIAL

This document is confidential. Do not disclose or use except as authorized.

True positive = truth standard positive & Lum cavity image positive
 False negative = truth standard positive & Lum cavity image negative
 True negative = truth standard negative & Lum cavity image negative
 False positive = truth standard negative & Lum cavity image positive

Figure 2: Definition of truth standard to evaluate the LUM Imaging System diagnostic performance.

When a therapeutic shave and re-excision are not available for a given orientation, the margin from the prior resected tissue of the corresponding orientation will be used as ground inferred truth for evaluation (Figure 3). The number of prior positive margins contributing to the ground inferred truth for a patient will not exceed the number of orientations with positive margins.

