The orientation of the tissue removed during a re-excision is typically noted in the pathology report and matches the orientation in which a positive margin was identified from the initial surgery. However, based on our prior experience there will be instances in which the orientation of the tissue removed during a re-excision is not specified. In cases of unclear orientation of the tissue removed during re-excisions, it will be assumed that the re-excision was intended to address only the orientations with positive margins and pathology findings from the re-excisions (tumor found/not found) will be applied to those orientations. Also, if there are two consecutive shaves during the re-excision from overlapping orientations, they will be considered as one.

If a mastectomy is performed as a follow-up surgery and no cancer is found in the mastectomy specimen, all the orientation will be considered as cancer negative for truth standard. If a mastectomy is performed and cancer is found but there is no indication on the orientation in which the cancer was found, the orientation in which a positive margin was identified in the initial lumpectomy will be considered as cancer positive for truth standard unless otherwise noted.

The diagnostic performance will be computed by using the hierarchical approach to populate the 2x2 contingency table (Table 1). The Youden Index will be reported but is not hypothesis-tested.

LUMICELL CONFIDENTIAL

This document is confidential. Do not disclose or use except as authorized.

Table 1: Definitions for 2x2 contingency table.

	Hierarchical Truth standard (+)	Hierarchical Truth standard (-)
LUM positive cavity signal (+)	True Positives	False Positives
LUM negative cavity signal (-)	False Negatives	True Negatives

$$\text{sensitivity} = \frac{\text{True Positives}}{\text{True Positives} + \text{False Negatives}}$$

$$\text{specificity} = \frac{\text{True Negatives}}{\text{True Negatives} + \text{False Positives}}$$

$$\text{Youden Index} = \text{sensitivity} + \text{specificity} - 1$$

[figure not shown]

Figure 3: Depiction of the prior margin assessment for the LUM signal in the cavity when no additional tissue from the cavity is available.

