3.2.3 Additional sensitivity and specificity analysis

In the pivotal study protocol, images of the cavity are being recorded with the LUM Imaging System before the surgeon removes any SOC shaves. These images are saved with the tumor detection inactive to prevent potentially influencing surgeon's decision to remove the SOC shave. This procedure was implemented to acquire additional data for a potential future use of the LUM Imaging System before removing SOC shaves. However, this procedure does not represent the initial intended use of the LUM Imaging System, more so with the tumor detection algorithm turned off. The initial intended use of the LUM Imaging System is after the SOC procedure including removal of SOC shaves, is completed. Thus, the primary analysis for sensitivity and specificity to support the co-primary endpoints will be done with imaging data collected after the SOC procedure is completed, that is, based on therapeutic shaves, second surgery and prior margin using a hierarchical approach as described in Table 1. As part of the pivotal trial analysis, a secondary evaluation of sensitivity and specificity will include the results from the LUM imaging of the cavity prior to removing SOC shaves.

LUMICELL CONFIDENTIAL

This document is confidential. Do not disclose or use except as authorized.

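### The second tier of the truth standard is named inconsistently, so cancer found in a second surgery not done for positive margins can be scored as a false negative, a true negative or not at all

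*Protocol*

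**What the plan says.** Protocol 3.3.3.2 ties the word *re-excision* to its reason: a procedure "following the primary lumpectomy because of positive margins found from the initial lumpectomy procedure". The SAP gives no definition of its own.

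The later-surgery tier is then worded in several ways:

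- **Tier 2, re-excision.** Protocol 15.2: "When a shave does not exist, then whether tumor is found in a re-excision surgery is considered as the truth standard". SAP 3.2.2 says the same.
- **Tier 2, mixed terms.** Protocol 15.2: "When the therapeutic shave is not available and the follow-up surgery is performed, only the pathology from the first-time re-excision" is used.
- **Tier 2, second surgery.** SAP 3.2.3, describing the primary analysis: "based on therapeutic shaves, second surgery and prior margin using a hierarchical approach".
- **Fall-back to the margin, second surgery.** SAP 3.2.2 and Protocol 15.2: the margin is the truth "When neither a shave nor a second surgery exists for a given orientation that was imaged".
- **Fall-back to the margin, re-excision.** SAP 3.2.2: "When a therapeutic shave and re-excision are not available for a given orientation, the margin from the prior resected tissue" supplies the truth. Protocol 15.2 has a matching sentence.

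Two further rules in SAP 3.2.2, mirrored in Protocol 15.2, deal with orientation. When the orientation of re-excised tissue is unclear, "it will be assumed that the re-excision was intended to address only the orientations with positive margins", and the findings go to those orientations. The mastectomy rule is asymmetric. "If a mastectomy is performed as a follow-up surgery and no cancer is found in the mastectomy specimen", every orientation becomes truth-negative. If cancer is found without a stated orientation, it goes to the orientation that had a positive margin, unless otherwise noted.

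**The concern.** A LUM-positive site is normally shaved and so settled at tier 1. A cancer missed by LUM has no LUM-guided shave, so the later-surgery tier is one of the main ways it can be recognized as a false negative. If some second surgeries fall outside that tier, co-primary sensitivity can lose false negatives.

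Such surgeries are foreseeable. For invasive cancer a positive margin means tumor on ink (Protocol 3.3.3.1), and subjects are followed until no further surgical intervention is required (Protocol 8.4). The same hierarchy drives the programmed count of 70 truth-positive events that ends enrollment (Protocol 15.3.3, SAP 4.5). The program must therefore adopt some reading, and the text does not say which.

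**Working it through.** **Step 1. Trace one record through the text.** Take an orientation with a negative LUM image, no shave and a negative margin. A second surgery is done for a reason other than positive margins, and pathology reports tumor at that orientation.

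- Tier 2 as *second surgery* (SAP 3.2.3): the tissue is admitted. Truth is positive, so the record is a **false negative**.
- Tier 2 as *re-excision* under 3.3.3.2, with the re-excision fall-back: the tissue is not admitted and the negative margin is the truth, so the record is a **true negative**.
- Tier 2 as *re-excision*, with the second-surgery fall-back: the tissue is not admitted and the margin is barred, so there is **no truth value**.

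One record has three possible outcomes. With a positive LUM image and no shave, the second reading would give a false positive instead.

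**Step 2. Remove the orientation from the report.** The cancer is assigned only to positive-margin orientations. This patient has none, so the cancer has nowhere to go. The same holds for a mastectomy that contains cancer, whereas a cancer-free mastectomy sets all orientations negative.

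**Step 3. Reproduce the plan's figure.** Inputs from Protocol 15.3.2 are 70 truth positives, 60% against 40%, exact binomial, one-sided 2.5%. The smallest r with P(X ≥ r | 70, 0.40) ≤ 0.025 is 37, with actual level 0.0199. Power is P(X ≥ 37 | 70, 0.60) = 0.909, which agrees with the stated 90%.

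**Step 4. Assume a number of affected records.** The documents give none. Suppose 2% to 5% of the 268 patients in Protocol 15.3.3 have such a surgery, and 20% to 30% of these have cancer at a LUM-negative orientation:

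- low: 268 × 0.02 × 0.20 = 1.1
- high: 268 × 0.05 × 0.30 = 4.0

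Both percentages are assumptions without a source in the documents.

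**Step 5. Effect on the estimate.** Move k records from true negative to false negative, with 42 true positives. Lower bounds are exact (Clopper-Pearson, 2.5%).

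| k | Sensitivity | Lower bound |
|---|---|---|
| 0 | 42/70 = 60.0% | 47.6% |
| 1 | 42/71 = 59.2% | 46.8% |
| 4 | 42/74 = 56.8% | 44.7% |
| 10 | 42/80 = 52.5% | 41.0% |
| 12 | 42/82 = 51.2% | 39.9% |

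From the planned result it takes about 12 such records to miss the 40% goal. Specificity hardly moves: (1021/152) × 268 gives about 1,800 negatives, and k = 5 changes 65.0% to 64.9%.

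**Step 6. Effect at the boundary.** 37/70 has a lower bound of 40.6% and passes; 37/71 has 39.9% and fails. For k = 1 to 3 only a count of 37 true positives changes conclusion, since 38/73 still passes at 40.04%. For k = 4, a count of 38 changes too (38/74, 39.4%). At 60% sensitivity with 70 events, P(X = 37) = 4.6% and P(X = 38) = 6.0%.

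**Step 7. Chance of passing at a true sensitivity of 40%.** If k misses are dropped from 70 + k positives, this is P(X ≥ 37 | 70 + k, 0.40): 2.0% (k = 0), 2.6% (1), 3.3% (2), 4.2% (3), 5.2% (4). Setting the apparent sensitivity to 0.40 × (70 + k)/70 with 70 counted events gives 2.5% (k = 1) and 3.9% (k = 3), the same direction.

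All of this treats tissues as independent. SAP 4.3.2 tests with GEE, so 37 of 70 is an illustration and not the SAP's pass rule.

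**The case against.** A reader might infer that the plan discards every cancer found in a second surgery done for another reason, and so has a built-in bias toward the device. The documents do not support that.

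- No sentence says such cancer is ignored. The second-surgery fall-back blocks the margin, SAP 3.2.3 names second surgery as the tier, and the mastectomy rule asks for no reason.
- The SAP does not repeat the 3.3.3.2 definition. In its secondary endpoints (SAP 3.3) it adds the positive-margin reason to items i and j and omits it from item k, the rate of cancer found in second surgeries.
- Data collection is not confined to re-excisions. Protocol 5.3.2 lists the source documents as examples, and item k needs second-surgery pathology in any case.

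Nor is every second operation at a margin-negative site affected. The definition concerns the procedure. In a patient re-operated for one positive margin, oriented tissue from her other sites still counts. Pure DCIS less than 2 mm from ink is already a positive margin, so that close-margin case is outside the gap.

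The hierarchy graphics (Protocol Figure 6, SAP Figure 2) are not readable in the copies reviewed and could settle the term. The assumed counts are unsupported by data, and any single reclassification flips a result that sits on the boundary.

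These points limit the scope and size. They do not remove the contradiction: the re-excision fall-back stands in both documents beside a sentence that gives a different answer, and the orientation rules have no answer for a patient without a positive margin.

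**Conclusion.** The point holds as a contradiction in the truth standard for two co-primary endpoints and for the event count, together with a gap in the orientation rules. It does not hold as a settled rule that scores missed cancers as true negatives. That is one of three readings, and the one that favors the device.

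The gap concerns only patients whose second surgery was not for positive margins. Under the assumed 1 to 4 records, sensitivity falls from 60.0% to between 59.2% and 56.8%, and the planned result still clears 40%. The conclusion changes only if the count lies at or just above the minimum needed to pass. This rests on assumed frequencies, an exact binomial test in place of GEE, and the wording available without the two figures.

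**What to change.** - In SAP 3.2.2 and Protocol 15.2, define tier 2 as pathology of the first second ipsilateral breast surgery of that orientation during study follow-up, whatever its reason. Use that one term in every tier sentence, in both figures and in the event-count program.
- State how cancer of unreported orientation is scored when no margin was positive, including cancer in a mastectomy.
- Report the number of such cases, with a sensitivity analysis that counts them as truth-positive.
- Make clear in Protocol 5.2.9.1 and 5.3.2 that pathology from all such surgeries is collected.
- Keep the 3.3.3.2 definition for the re-excision rate endpoints only.

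The cost is wording in a few sections, a few more existing pathology reports and possibly a slightly lower sensitivity. Patient care does not change.
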